14.10 Interim Analysis

Two interim analyses after 40 and 80 patients are planned according to the Pocock adjusted levels $\alpha_p = 0.0221$. Based on the results of an interim analysis the sample size can be adjusted (Lehmacher, Wassmer, 1999). There are no prespecified futility margins, but the DSMB can recommend stopping the study in the case of insufficient interim results.

14.11 Subject disposition

Subject disposition data (number of subjects screened, assigned to treatment, completing each assessment and the primary reason for withdrawal, number of each analysis population, subjects excluded from each analysis population) will be summarized overall for all subjects.

A by-subject listing will be provided showing all screened subjects who were not eligible to be assigned to treatment together with the reason for non-eligibility.

Number and percentage of subjects assigned to treatment who discontinued the study prematurely will be summarized for the overall population and stratified by reason for study discontinuation. Multiple reasons are possible.

A by-subject listing will be provided showing for all subjects assigned to treatment whether they completed study (yes/no), the reason(s) for study discontinuation (where applicable), and the dates of:

- the informed consent,
- the first application of study medication,
- the last application of study medication,
- discontinuation / withdrawal, where applicable.

14.12 Extent of exposure

For each subject, the individual study duration will be calculated in days as " $d_{lastVisit} - d_{Visit\ 1} + 1$ ", where $d_{lastVisit}$ is the date of last visit documented and $d_{Visit\ 1}$ is the date of Visit 1, respectively.

Exposure to IMP will be summarized descriptively as (1) number of applications made and (2) study duration (in days).

Summary statistics will be tabulated for the safety population.

	Trial Substance:	Ruconest®	Study No.: C1 6201 PROTECT-COVID-19-US
	Short Title:	Ruconest®: Prevention of severe SARS-CoV-2 infection in hospitalized patients with COVID-19	Sponsor: Pharming Technologies B. V.

14.13 Medical history

Diseases will be coded according to MedDRA. Details of the Medical History will be listed.

14.14 Previous and concomitant medications

Medications will be coded by means of DRL (WHO-DD).

A previous medication is a medication used only before the date of first dose of study medication (medication end date < date of first dose of study medication). All other medications are concomitant.

If medication start and/or stop dates are missing or partial, the dates will be compared as far as possible with the date of first dose of study medication. Medications will be assumed to be concomitant, unless there is clear evidence (through comparison of partial dates) to suggest that the medication started and stopped prior to the first dose of study medication. If there is clear evidence to suggest that the medication stopped prior to the first dose of study medication, the medication will be assumed to be previous.

Medications starting after the completion/withdrawal date will be listed but will not be classified or summarized.

Information on previous and/or concomitant medication will be listed with flags to differentiate previous and/or concomitant medications.

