3.6 Explanation for Choice of Comparator

Currently, no approved or effective treatment options for COVID-19 infections exist. Participants will either receive rhC1INH plus SOC or only SOC. SOC may include treatment for underlying comorbidities and management of COVID-19 symptoms. Importantly, local treatment protocols including drugs with perceived benefits in COVID-19 infections such as lopinavir/ritonavir are allowed as long as they are declared as SOC. In order to facilitate patient recruitment in a time of restricted human and financial resources, and because of an objective primary endpoint, a placebo group will be omitted.

Diphenhydramine, hydroxychloroquine, and azithromycin are associated with prolongation of the cardiac QT interval, and subsequent increased risk of fatal cardiac arrhythmia.

Cardiovascular monitoring will be conducted in severely-ill subjects receiving multiple drugs on a case-by-case adjudication of any prolongation of QT intervals to evaluate the benefit-risk of continued participation in the clinical study.

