5.3 Other Outcomes of Interest

- Changes on the WHO Ordinal Scale from baseline over 14 days
- Length of hospital stay until day 28 in survivors.
- Proportion of participants progressing to mechanical ventilation on day 7 and day 14
- Proportion of participants requiring ICU treatment on day 7 and 14
- Length of ICU stay until day 28
- Ventilator-free days until day 28
- All-cause mortality (time from randomization to death within 4 weeks)
- Changes in biomarker levels until day 14: CRP, LDH, D-dimer, ferritin, IL-6, lymphocyte count
- Time to virological clearance of SARS-CoV-2 by PCR from upper or lower respiratory tract samples (time from enrollment to first of 2 negative assays at least 12 hours apart)
- Proportion of patients receiving additional anti-inflammatory treatment such as tocilizumab or immunoglobulins within 14 days
- Time to defervescence (temperature $<38.0^{\circ}\text{C}$ sustained for at least 48 hours)
- Time to clinical improvement (defervescence, normalization of oxygen saturation ($>93\%$) and respiratory rate) until day 28
- Duration of supplemental oxygen until day 28
- In a subgroup of patients, the pharmacokinetics and pharmacodynamics of rhC1INH in COVID-19 patients will be characterized by measuring the concentration of rhC1INH and the activity of C1-INH and proteins (such as C3, C4).

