7.1 Eligibility Criteria

Participants fulfilling all of the following inclusion criteria are eligible for the study:

- Informed Consent as documented by signature,
- Male or Female age 18-85 years,
- Admitted to the hospital because of confirmed COVID-19 infection (by a positive SARS-CoV-2 PCR result),
- Expected to remain an inpatient over the next four (4) calendar days from time of enrollment,
- Evidence of pulmonary involvement on CT scan or chest X-Ray of the chest (e.g. ground glass opacities),
- Symptom onset within the previous 10 days OR shortness of breath within the previous 5 days. Symptoms include fever or one respiratory symptom (patients presenting later may have already progressed to an inflammatory state that is potentially not amenable to C1INH treatment). Respiratory symptoms include cough, sore throat, hemoptysis, shortness of breath, runny nose, or chest pain and
- at least one additional risk factor for progression to mechanical ventilation: 1) arterial hypertension, 2) >50 years, 3) obesity (BMI>30.0 kg/m²), 4) history of cardiovascular disease, 5) chronic pulmonary disease, 6) chronic renal disease, 7) C-reactive protein of >35mg/L, 8) oxygen saturation at rest in ambient air of <94%. Cardiovascular disease includes a history of coronary artery disease, cerebrovascular disease, peripheral artery disease, rheumatic heart disease, congenital heart disease and of

recent (< 3 months) deep vein thrombosis or pulmonary embolism. Chronic pulmonary disease includes a history of chronic obstructive pulmonary disease, asthma, occupational lung disease, interstitial lung disease or of pulmonary hypertension. Chronic renal disease is defined as a history of an estimated glomerular filtration rate (according to the Chronic Kidney Disease Epidemiology Collaboration equation) < 60ml/min/1.73 m² for at least three months.

*Also refer to the WHO definition for additional Cardiovascular diseases

The presence of any one of the following exclusion criteria will lead to exclusion of the participant:

- Contraindications to the class of drugs under study (C1 esterase inhibitor), e.g. known hypersensitivity or allergy to class of drugs or the investigational product,
- Treatment with tocilizumab or another IL-6R or IL-6 inhibitor (within 24 hours) prior to enrollment,
- History or suspicion of allergy to rabbits,

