8.1.2 Control Intervention (standard/routine/comparator treatment / medical device)

Participants in the control arm will receive SOC treatment according to local guidelines.

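### SAP 14.14 sorts previous from concomitant medication by the first dose of study drug, a date that SOC patients do not have, so the flag is not comparable between arms

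*SAP*

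**What the plan says.** SAP section 14.14 defines the two classes by a single reference date. A drug is previous if its end date falls before the first dose: "A previous medication is a medication used only before the date of first dose of study medication". The default follows at once: "All other medications are concomitant". Where medication dates are missing or partial, the same reference applies: "the dates will be compared as far as possible with the date of first dose of study medication". In that case too the drug counts as concomitant unless there is clear evidence that it had stopped earlier. There is one exception: "Medications starting after the completion/withdrawal date will be listed but will not be classified or summarized". The output named in the section is a listing with flags for the two classes. SAP section 14.4 likewise says that concomitant therapies will be listed.

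On who has a first dose, Protocol section 8.1.2 says: "Participants in the control arm will receive SOC treatment according to local guidelines". Protocol section 3.6 rules out a dummy dose: "because of an objective primary endpoint, a placebo group will be omitted". Under Visit 2 in Protocol section 9.2.1, rhC1INH goes to the active group only. Neither document gives SOC patients another reference date for this classification.

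**The concern.** A classification by date works only if every patient has the date. Here one arm lacks it by design, and the default decides the class instead. The resulting error follows treatment assignment and is not spread evenly over the trial.

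The situation can arise in practice. Prior and concomitant medications are recorded from Visit 1 (Protocol section 9.1). SAP section 5.4 collects drugs taken before admission and off-label COVID-19 drugs. Eligibility also leaves room for relevant earlier treatment: the IL-6 criterion excludes only "Treatment with tocilizumab or another IL-6R or IL-6 inhibitor (within 24 hours) prior to enrollment", so a dose given before that window is allowed.

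What is at stake is the description of background treatment. The trial is open-label, and the comparator is local SOC, which can differ by site. A reader will want to know whether other COVID-19 drugs were balanced between the arms. A flag that carries a different meaning in each arm cannot answer that.

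**Working it through.** There is no stated figure to reproduce, because the point is about a rule and not about sample size or alpha. The check applies the rule as written to identical drugs in three kinds of patient.

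**Inputs**
- Rule (SAP 14.14): previous if end date < first-dose date; otherwise concomitant; not classified if started after completion or withdrawal.
- First-dose date: Day 0 for a dosed rhC1INH patient; none for an SOC patient; none for a patient randomised to rhC1INH but never dosed.
- Allocation (SAP section 2): 80 rhC1INH and 40 SOC, 120 in total.

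**Rule as written**

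| Drug ended | rhC1INH, dosed | SOC | rhC1INH, never dosed |
|---|---|---|---|
| Day −40 | previous | concomitant | concomitant |
| Day −1 | previous | concomitant | concomitant |
| Day 0 | concomitant | concomitant | concomitant |
| Day 4 | concomitant | concomitant | concomitant |
| End date missing | concomitant | concomitant | concomitant |

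The columns differ only in the first two rows, that is, for drugs that ended before Day 0. A drug started after completion or withdrawal is left unclassified in all three.

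The partial-date rule behaves in the same way. If only the month of stopping is known and it precedes the month of Day 0, a dosed rhC1INH patient's drug can be shown to be previous. For an SOC patient there is nothing to compare it with, so the default applies.

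**Reach.** The reference date is missing for the whole planned control arm: 40 / 120 = 33% of patients, plus any rhC1INH patient who is never dosed. The documents do not say how many patients will have a drug that ended before Day 0. If that share is p, the expected number of affected controls is 40 × p. Purely as an assumption, p = 5% gives 0.05 × 40 = 2 controls and p = 20% gives 0.20 × 40 = 8. The corresponding number among dosed rhC1INH patients with complete dates is 0.

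**Same drugs, randomisation (Day 0) as reference.** The drugs that ended on Day −40 and Day −1 become previous, and the other three become concomitant, in all three kinds of patient. The difference between the columns disappears.

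**The case against.** The strongest reply is that little depends on this flag. The only outputs specified are listings. No table, rate or between-arm test of concomitant medication is planned, and the efficacy analyses in SAP sections 14.5.1 and 14.5.2 do not use the class. That stands, and it limits the point. It does not remove it: a listing flag that means different things in the two arms still misleads. The remark that post-completion drugs will not be summarised also suggests that a summary of the others may be made.

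A second reply is that the text can be read as silent, rather than wrong, for patients without a dose, and that Day 0 is an obvious substitute because Visit 2 is already the baseline in both arms (SAP 5.6). The substitute is indeed at hand, but the section does not use it. On the silent reading, someone would have to choose the rule later with treatment assignment known.

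A third reply is that treatment before enrolment is also captured among the baseline and history variables in SAP 5.4. That is true, so the flag is not the only way to judge balance.

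A reader might go further and infer that the rule biases an outcome in favour of rhC1INH, namely "Proportion of patients receiving additional anti-inflammatory treatment such as tocilizumab or immunoglobulins within 14 days", by counting a control's earlier tocilizumab as escalation on study. The documents do not support this. No section derives that outcome from the flag. Protocol section 9.1.3 records it separately over its own 14-day period, Protocol section 8.6 describes escalation as something done during the trial in patients who deteriorate, and SAP 14.5.2 treats the other outcomes of interest as descriptive and exploratory.

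**Conclusion.** The rule is wrong as written, with a limited consequence. For SOC patients and undosed rhC1INH patients, drugs stopped before enrolment are flagged concomitant; in dosed rhC1INH patients the same drugs are flagged previous. The missing date affects all 40 planned controls. The number of misflagged drugs cannot be derived from the documents and depends on how many had ended before Day 0.

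Two wider readings should be avoided. It is not every drug in the control arm, since continuing drugs are flagged correctly and drugs started after completion or withdrawal are not classified. Nor is it the control arm alone, since undosed rhC1INH patients are affected in the same way.

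The conclusion rests on a literal reading of the default class and on study medication meaning rhC1INH, which is how both documents use the term. The primary and secondary efficacy results are untouched. The medication flag, and any summary built on it, is not comparable between the arms until the reference date is changed.

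**What to change.** In SAP 14.14, replace the first-dose reference with the date of randomisation (Day 0) wherever it appears, including in the rule for missing and partial dates. State that this applies to all randomised patients in both arms, whether or not they were dosed.

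The cost is a change of SAP wording. Every patient in the FAS/ITT population has a randomisation date, so no new data are needed and trial conduct does not change. Randomisation and first dosing are both scheduled for Day 0 (Protocol section 9.1), so a comparison by calendar date leaves dosed rhC1INH patients almost unchanged. The small downside is that a drug stopped between randomisation and a later first dose becomes concomitant in the rhC1INH arm. SAP section 1 says that the plan is finalised after the blind review, so the change can be made before then.

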14.14 Deviations from the original statistical plan

Deviations from the planned analyses will be discussed by the Sponsor and the biostatistician and consequently justified and reported in the final reports and the publications.

15 VISIT WINDOWS

All data will be organized and analyzed according to the scheduled visits outlined in the protocol.

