- A negative pregnancy test before study entry/randomization. We expect the rate of female patients of childbearing age who may become pregnant to be <10% of all patients potentially eligible for this study. Due to the short treatment period (4 days) and half-life of rhC1INH (2.5 hours) an effective means of contraception is not mandatory during the hospitalization treatment phase. At least one method of contraception (oral contraceptives, barrier methods, approved contraceptive implant or abstinence) is required for the entire follow up study period
- Concomitant Interventions (treatments)

All participants will receive standard supportive care established at the sites which may include off-label use of certain drugs that are deemed to be effective in COVID-19 (e.g. hydroxychloroquine, lopinavir/ritonavir, prophylactic anticoagulation). In addition, escalation of treatment with off-label use of certain drugs (e.g. tocilizumab) in deteriorating participants is allowed during the trial. Randomization will be stratified by site to compensate for different standards of supportive care. Off-label use of drugs for the treatment of COVID-19 will be recorded in the CRF. Escalation of treatment is one outcome of interest.

Patients are allowed to use all their regular medication during the trial. In addition, patients will receive all drugs required for the treatment of COVID-19 or its consequences. The care of the participant will remain unaffected by inclusion into the study or by study group assignment.

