9.1.3 Assessment of Other Outcomes of Interest

- The following assessments will be performed during the study: changes in WHO ordinal scale, ICU admission/discharge date, mechanical ventilation start/end date, admission/discharge date, all-cause mortality within 4 weeks.
- Supportive interventions provided to study subjects in addition to ventilatory support (e.g., the use of prone ventilation, high-frequency oscillatory ventilation (HFOV), paralytics, pulmonary vasodilators).
- The receipt of additional anti-inflammatory treatments such as tocilizumab will be recorded within 14 days.
- Vital signs will be recorded until discharge to determine the time to defervescence and clinical improvement.
- For the analysis of virological clearance of SARS-CoV-2, samples from the upper or lower respiratory tract will be collected at baseline (if not already performed on admission) to confirm SARS-CoV-2 infection and again on day 4-7 and day 14/discharge. Subsequently, samples will be analysed at the central laboratory of the study site using a quantitative assay according to validated standard in-house procedures. A negative result will be confirmed by a second test at least 12 hours apart.
- For the analysis in changes of biomarker levels CRP- LDH, D-dimer, IL-6 and lymphocytes will be measured in blood samples collected on day 0, 1-3 every day afterwards until day 14 or discharge. Blood samples will be sent to and analysed by validated methods in the central laboratory of respective study sites according to

standard in-house procedures.

- For the analysis of inflammatory proteins and cytokines blood samples will be collected on day 0, and daily until day 14 or discharge. For the analysis of rhC1INH pharmacokinetics (C1INH activity and concentration), blood samples will be collected at baseline, 5-10 minutes after the first administration and again immediately before and 5-10 minutes after a subsequent administration on day 1.

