- Routine laboratory tests will be performed daily during admission according to standard procedures, and should include a set of hematology, coagulation and biochemistry parameters. Additionally, blood (7ml) for analysis of ferritin, IL-6, D-Dimer, C1INH concentration will be collected at the same time point.
- Monitoring of prolonged QT intervals in severely-ill subjects receiving multiple drugs.
- Measurement of oxygenation levels.
- Monitor your heart rhythms in severely-ill subjects receiving multiple drugs
- Assessment of AEs and concomitant medications

Visit 5, Intervention period (Day 3-13 during hospital admission)

- Assessment of physical examination
- Completion of treatment with rhC1INH (150 U/ml) at a 50 U/kg dose (max dose of 4200 U) every 12 hours (8 doses in total) in the active treatment group as per treatment schedule. The time of dosing and the dose will be recorded. (Treatment to be administer at Visit 5 on Day 3 ONLY)
- Assessment of vital signs including respiratory rate.
- Assessment of WHO ordinal scale and need for oxygen supplementation.
- Documentation of ICU admission and/or non-invasive or invasive ventilation
- Routine laboratory tests will be performed daily during admission according to standard procedures, and should include a set of hematology, coagulation and biochemistry parameters. Additionally, blood (7ml) for analysis of ferritin, IL-6, D-Dimer, C1INH concentration will be collected at the same time point. and collection of blood for the analysis of complement proteins (C3 & C4).
- Virological assessment (SARS-CoV-2 PCR in respiratory specimen) should be performed on day 4-7 (according to local standard).
- Monitoring of prolonged QT intervals in severely-ill subjects receiving multiple drugs.

- Measurement of oxygenation levels.
- Monitor your heart rhythms in severely-ill subjects receiving multiple drugs
- Assessment of AEs and concomitant medications

Visit 6, Follow-up (Day 14 (+/-2 days) or at discharge)

- Physical examination including body weight.
- Assessment of vital signs including respiratory rate.
- Assessment of WHO ordinal scale and need for oxygen supplementation
- Documentation of ICU admission and/or non-invasive or invasive ventilation

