3 TIME SCHEDULE

The study consists of 7 visits: screening visit (Visit 1, Day -1), and intervention period visits Visit 2 (Day 0), Visit 3 (Day 1), Visit 4 (Day 2), Visit 5 (Day 3-13 during hospital admission), and follow-up visits Visit 6 (Day 14 ± 2 days or discharge) and Visit 7 (Week 4 ± 3 months). A detailed schedule of assessments is presented in the Study Protocol, Final Version 3.0 dated 12 January, 2021 Chapter 9.1.

	Trial Substance:	Ruconest®	Study No.: C1 6201 PROTECT-COVID-19-US
	Short Title:	Ruconest®: Prevention of severe SARS-CoV-2 infection in hospitalized patients with COVID-19	Sponsor: Pharming Technologies B. V.

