5.1.3 Other Outcomes of Interest

- Changes on the WHO Ordinal Scale from baseline over 14 days.
- Length of hospital stay until day 28 in survivors.
- Proportion of participants progressing to mechanical ventilation on Day 7 and Day 14.
- Proportion of participants requiring ICU treatment on Day 7 and 14.
- Length of ICU stay until Day 28.
- Ventilator-free days until Day 28.
- All-cause mortality (time from randomization to death within four weeks).
- Changes in biomarker levels until Day 14: CRP, LDH, D-dimer, ferritin, IL-6, lymphocyte count.
- Time to virological clearance of SARS-CoV-2 by PCR from upper or lower respiratory tract samples (time from enrollment to first of 2 negative assays at least 12 hours apart).
- Proportion of patients receiving additional anti-inflammatory treatment such as tocilizumab or immunoglobulins within 14 days.
- Time to defervescence (temperature $<38.0^{\circ}\text{C}$ sustained for at least 48 hours).
- Time to clinical improvement (defervescence, normalization of oxygen saturation ($>93\%$) and respiratory rate) until Day 28.
- Duration of supplemental oxygen until Day 28.

In a subgroup of patients, the pharmacokinetics and pharmacodynamics of rhC1-INH in COVID-19 patients will be characterized by measuring the concentration of rhC1-INH and the activity of C1-INH and inflammatory cytokines and proteins (such as C3, C4).

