5.6 Derived variables

For quantitative variables the absolute changes from baseline (Visit 2) will be determined.

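### Analysing biomarkers by scheduled visit would combine different study days according to length of stay, because Visit 6 is Day 14 or discharge and Visit 5 covers Days 3-13 with no rule for choosing a value

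*SAP*

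**What the plan says.** SAP section 15 gives one rule for all data: "All data will be organized and analyzed according to the scheduled visits outlined in the protocol". The visits it refers to are in SAP section 3. Visits 2, 3 and 4 are the single Days 0, 1 and 2, followed by "Visit 5 (Day 3-13 during hospital admission), and follow-up visits Visit 6 (Day 14 ± 2 days or discharge"). Protocol section 9.2.1 uses the same definitions and, under Visit 6, requires a sample on the day of discharge if no routine test was done that day.

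The outcome in SAP section 5.1.3 is "Changes in biomarker levels until Day 14: CRP, LDH, D-dimer, ferritin, IL-6, lymphocyte count". Protocol section 9.1.3 has blood drawn on Days 0 to 3 and then "every day afterwards until day 14 or discharge". SAP section 5.6 sets the derived quantity: "For quantitative variables the absolute changes from baseline (Visit 2) will be determined". SAP section 14.5.2 gives the other outcomes of interest descriptive and exploratory statistics only. SAP section 14.6 summarises vital signs as means per visit and change from baseline.

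**The concern.** A visit label is a usable time axis only if it means about the same study day for every patient. That holds for Visits 2 to 4 but not for Visits 5 and 6. A Visit 6 value may come from Day 5 in a patient who went home early and from Day 14 in one who is still ill. A patient's Visit 5 may hold one value or eleven.

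Discharge happens after randomisation, and live discharge is part of a secondary endpoint that the drug is meant to improve (SAP section 5.1.2). If stay differs between arms, the sampling day under the same label differs too. A marker that changes over time can then differ between arms at Visit 6 even when its daily course is identical. The overall objective (Protocol section 4.1) is benefit through limiting the inflammatory response, so these markers will be read as evidence on mechanism, even though they are exploratory.

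**Working it through.** **1. Width of the visits.** Visit 5 runs from Day 3 to Day 13: 13 − 3 + 1 = 11 study days, so up to 11 daily values per patient. Visit 6 is Day 14 ± 2, that is Days 12-16, or any earlier discharge day. Days 12 and 13 fit both visits.

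**2. Search for a rule that resolves this.**
- The schedule footnote on the worst value recorded selects within a single day, not across Days 3-13. In the protocol it is attached to vital signs.
- Last observation carried forward (SAP section 14.9) applies to the primary variable only.
- SAP section 14.5.2 has no by-day or repeated-measures rule for other outcomes.
- The outcome wording (until Day 14) and the daily sampling would permit a by-day analysis, but no SAP text specifies one.

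**3. Size, as an illustration.** The plan gives no figure to reproduce, and every input here is assumed. The marker falls by a fraction r per day (10-20%) in both arms, so the drug has no effect on it. The discharge day D is lognormal with log-SD 0.5, rounded to whole days and confined to Days 4-14. Median stay is 6 days on rhC1INH and 8 on SOC. D does not depend on the marker. The Visit 6 sample is taken on day D.

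Ratio of Visit 6 geometric means (rhC1INH/SOC) = exp[(mean D on rhC1INH − mean D on SOC) × ln(1 − r)].

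Absolute change, as a share of baseline: fall = 1 − mean of (1 − r)^D.

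| Days outside 4-14 | Mean D | Ratio, r = 10% | Ratio, r = 20% | Fall, r = 10% | Fall, r = 20% |
|---|---|---|---|---|---|
| moved to 4 or 14 | 6.82 v 8.54 | exp(−1.72 × −0.105) = 1.20 | exp(−1.72 × −0.223) = 1.47 | 49.2% v 56.9% (gap 7.7) | 74.2% v 81.0% (gap 6.8) |
| dropped | 6.97 v 8.04 | exp(−1.07 × −0.105) = 1.12 | exp(−1.07 × −0.223) = 1.27 | 50.4% v 55.3% (gap 5.0) | 75.8% v 80.2% (gap 4.4) |

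Gaps are in percentage points of baseline, taken before rounding. With median stay 7 versus 8 days, the ratios are 1.09-1.20 (moved) or 1.06-1.12 (dropped), and the gaps are about 3-4 or 2 points.

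**4. A second discharge model.** Here discharge day is 2 plus a Poisson count, capped at Day 14, and the log marker falls by 0.05-0.15 per day. With equal mean discharge day (7 v 7) the ratio is 1.00 at both visits. With 6 v 8 it is 1.10-1.35 at Visit 6 and 1.05-1.14 at Visit 5, if each patient's Visit 5 values are averaged. In these models the artefact comes entirely from the difference in stay.

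**The case against.** **The SAP does not order pooling.** A reader might infer that the plan averages or selects across Days 3-13. It does not say so. The Day 7 primary score itself falls inside Visit 5 and is defined by day, so section 15 cannot sensibly mean one value per visit number for everything. This stands for Visit 5, where the fault is silence. It does not rescue Visit 6, whose definition itself puts discharge-day and Day 14 values under one label.

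**The outcome is low-tier.** Biomarkers are other outcomes of interest, described without a formal test, and no alpha or decision rests on them. This stands and limits the importance of the point.

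**The direction is not established.** A reader might infer that a working drug would look worse on biomarkers, or that a real biomarker effect would be hidden. The illustration cannot show either. It assumes no drug effect on the marker and makes discharge independent of it. Patients usually leave hospital when they improve, which would tend to bring discharge-day values in the two arms together. The ratios also look larger than the gaps on the absolute-change scale that the SAP specifies.

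**Escalation treatment.** The protocol states that "escalation of treatment with off-label use of certain drugs (e.g. tocilizumab) in deteriorating participants is allowed during the trial", and a reader might infer that IL-6 and CRP are distorted unequally between arms. The documents do not show an imbalance. The two of five compassionate-use patients who received tocilizumab (Protocol section 3.4) were uncontrolled and on a different regimen.

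**By-day analysis is not a full cure.** Sampling stops at discharge, so later days describe only those still in hospital. This stands, but showing the numbers sampled makes it visible.

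**Conclusion.** The point holds as a gap in the analysis specification for exploratory biomarkers and vital signs. Followed as written, SAP section 15 with the Visit 6 definition compares values whose study day depends on a post-randomisation event that treatment may affect. For Visit 5 the plan leaves open which of up to 11 values counts. The between-arm comparison could be biased, but neither size nor direction can be derived from the documents. On the assumed inputs (6 v 8 days, 10-20% daily fall), the Visit 6 ratio is about 1.1-1.5, or about 4-8 percentage points of baseline in absolute change. With equal stay it vanishes.

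It would be wrong to read this as a threat to the main results. The Day 7 score and the tested secondary endpoints are defined by day or over 14 days, and nothing here shows that they are affected.

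**What to change.** In SAP section 15:

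- Assign each daily laboratory biomarker and vital-sign value to its study day, and summarise change from Day 0 by study day to Day 14. Show the number still hospitalised and the number sampled per arm on each day.
- Report discharge-day values separately from Day 14 values.
- Highlight Day 3 without replacing the outcome that runs until Day 14. Patients are enrolled on Day −1 and expected to stay four further calendar days (Protocol sections 7.1 and 9.2.1), so Day 3 is the latest day on which nearly all should still be inpatients. Note that this sample precedes that day's first dose: with two doses on each of Days 0-2, it reflects six of the eight.

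A summary of IL-6 and CRP that omits values after the first IL-6 or IL-6R inhibitor dose is at most an optional supplement beside the all-values summary. It should be labelled as selective, because it removes values on the basis of deterioration after randomisation.

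The cost is SAP wording and a few extra tables, with no new data. SAP section 1 has the SAP finalised after blind review, so the change can still be made, preferably before any results by arm are seen. The remaining limitation is that later days still describe only patients who remain in hospital.
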